The questionnaire will allow allocation of RANCH HAND personnel into those with symptoms on questionnaire, indicated by RS, and those without, \overline{RS} . Similarly, the control individuals will be placed into symptomatic, indicated CS, and asymptomatic, \overline{CS} groups.

The physical examination performed on individuals from R and C will allow estimation and comparison of rates of physical findings in these groups. Rates of abnormal physical findings can be symbolically indicated as f_R and f_C for RANCH HAND and control groups respectively. Comparison of these rates is very important and details will be discussed below.

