28 NOV 1979

AIR FORCE WORKING PAPER

DESIGN SCHEMATIC

Let f_{RS} be the rate of physical findings among RANCH HAND personnel with findings by questionnaire and let $f_{R\bar{S}}$ be the rate of physical findings among RANCH HAND people with no findings on their questionnaire. For most disease processes it would be expected that f_{RS} should be a larger rate than $f_{R\bar{S}}$. If f_{RS} is observed to be equal to or less than $f_{R\bar{S}}$, an interpretation of over-reporting may be warranted, although the possibility of sub-clinical disease is recognized. Rates f_{CS} and $f_{C\bar{S}}$ will also be estimated, and comparisons between f_{RS} , f_{CS} , $f_{R\bar{S}}$ and $f_{C\bar{S}}$ will be accomplished.

The eight rates m_R' , m_C' , s_R , s_C , f_{RS} , $f_{R\bar{S}}$, f_{CS} , $f_{C\bar{S}}$ and their refinements fully characterize this study. As depicted in Figure 6, "vertical comparisons of these rates provide relative risks m_R'/m_C' , s_R/s_C , f_R/f_C , f_{RS}/f_{CS} and $f_{R\bar{S}}/f_{C\bar{S}}$ which are of central importance in defining herbicide effects. "Horizontal comparisons" relate f_R to s_R , f_{RS} to $f_{R\bar{S}}$, f_C to s_C and f_{CS} to $f_{C\bar{S}}$. Specifically, the ratio f_R/s_R is the ratio of physical findings to reported symptoms in the RANCH HAND population. This ratio may be contrasted with the ratio f_C/s_C and if f_R/s_R is less than f_C/s_C overreporting can be inferred. Likewise, if f_{RS} is less than $f_{R\bar{S}}$, over-reporting is further suggested. A comparison of $f_{RS}/f_{R\bar{S}}$ to $f_{CS}/f_{C\bar{S}}$ contrasts the odds of findings given symptoms in the RANCH HAND population with the odds of findings given symptoms in the control group. If these odds are lower in the RANCH HAND group, over-reporting is again implied. However, the existence of sub-clinical disease as the cause of these ratios cannot be excluded.

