When there is non-differential misrepresentation, that is, when the sensitivity and the specificity are the same among the exposed and nonexposed, the bias induced in the estimate of relative risk will be toward the null value. The situation is summarized by Figure 8.

FIGURE 8

[figure not shown]
MISREPRESENTATION IN RANCH HAND II

		TRUE STATUS					
		EXPOSED			NONEXPOSED		
		S	\bar{S}	TOTAL	S	\bar{S}	TOTAL
REPORTED STATUS	S	a	b	a + b	e	f	e + f
	\bar{S}	c	d	c + d	g	h	g + h
		a + c	b + d	n	e + g	f + h	n

Using this representation, the true relative risk is $(a+c)/n \div (e+g)/n$, and the apparent relative risk is $(a+b)/n \div (e+f)/n$. Figure 9 provides a graphic representation of how apparent relative risk varies as a function of specificity. For this curve, the true relative risk is 2 with the exposed population having a symptom incidence of 0.1 and the nonexposed population having a symptom incidence of 0.05 (Copeland et. al. 1977). The effect of nondifferential false reporting on the odds ratio is nearly as severe as that shown in Figure 9 for relative risk. A technique does exist for correcting the estimate of relative risk to account for false reporting, but the technique requires knowledge of the sensitivity and specificity of the classification scheme, knowledge that may not exist in this study. It should be noted that since the above remarks are concerned with relative risk, the number n of subjects in each group is irrelevant, as the results shown are independent of n.

If the false reporting is differential, an estimate of relative risk that is biased away from the null value can result. This will occur in situations in which the RANCH HAND personnel and controls do not misrepresent their symptoms in the same manner (Copeland et. al. 1977). Thus the "true" outcomes of herbicide exposure may be distorted depending upon the degree and direction of misrepresentation.

FIGURE 9
APPARENT RELATIVE RISK VERSUS
SPECIFICITY

C. Analysis of Mortality Data

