False positive response is anticipated as the primary bias operating in this study. Compensation issues arising from individual claims to the VA or from class action suits, heightened health concern generated by extensive publicity, disenchantment with military service, and the simple desire to please the interviewer may introduce positive responses that exceed the study's ability to correct or adjust. False negative response will also operate, and such bias is even more difficult to assess than the spurious response in a positive direction. Significant factors in this direction include: issues of patriotism and loyalty, personal conviction as to the propriety of the defoliation program and their participation in it, the strong virility orientation of the pilot/aircrew population (particularly with reference to questions of libido and fertility), personal inconvenience caused by study participation, errors of memory, and fear of the adverse effects on career goals that abnormal physical examination results could produce (a significant problem for active civilian and military pilots).

(2) Pending Retirement Bias

The military retirement system also creates a potential source of bias. A "pending-retirement phenomenon" occurs when personnel who are approaching the end of their careers exaggerate their symptoms so that they may become eligible for disability benefits.

(3) Corrective Measures

The primary correction technique for questionnaire response bias will be a carefully constructed and standardized physical examination. Multiple verification and bias indicator questions will be designed and included in the initial questionnaire. Memory verification will be conducted by cross-referencing responses

to medical and personnel records. Detailed statistical correlations between the questionnaire responses and the physical examination results will be conducted. All telephone interviews and physical examinations will be conducted on a "blind" basis to the maximum extent possible. Self-administered and group-administered questionnaires, which would allow for uncontrolled response changes, will not be conducted. Models of anticipated biases and their estimated impact on the study will be attempted prior to the final analysis of any phase in order to justify the analytic methods used. Conclusions drawn from this study will be predicated and coupled to a bias estimate.

E. Interview Bias

(1) Problem

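### Two of the five ratios that Section VI.A uses to define the herbicide effect, f_RS/f_CS and f_RSbar/f_CSbar, condition on self-reported symptoms and so do not estimate it

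*Protocol*

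**What the plan says.** Section VI.A of the protocol sorts men by questionnaire: "The questionnaire will allow allocation of RANCH HAND personnel into those with symptoms on questionnaire" and those without, and likewise for controls. It defines f_RS to "be the rate of physical findings among RANCH HAND personnel with findings by questionnaire". The rates f_RSbar, f_CS and f_CSbar follow the same pattern, where the suffix bar marks men who reported no symptoms. Unconditional rates are defined as well: "Rates of abnormal physical findings can be symbolically indicated as f_R and f_C for RANCH HAND and control groups respectively".

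The design schematic then forms five vertical (RANCH HAND over control) ratios, called relative risks: m_R'/m_C' for mortality, s_R/s_C for symptoms, f_R/f_C for findings, and f_RS/f_CS and f_RSbar/f_CSbar for findings within symptom strata. All five are given the same standing, as ratios "which are of central importance in defining herbicide effects". The horizontal comparisons in the same section, such as f_RS against f_RSbar, are used to detect over-reporting.

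Section VIII.D states: "False positive response is anticipated as the primary bias operating in this study". Section VI.B(2) says that misreporting can bias a relative risk away from the null when it is differential: "This will occur in situations in which the RANCH HAND personnel and controls do not misrepresent their symptoms in the same manner". That section deals with the relative risk of the symptom itself. No section warns about the two symptom-stratified vertical ratios.

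**The concern.** Reported symptoms come after exposure. They are a consequence of disease, of willingness to report, and possibly of exposure through either route. A ratio of finding rates within a symptom stratum compares groups that have already been sorted by that consequence. Two things can go wrong.

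- If healthy RANCH HAND men report false symptoms more often than healthy controls, they enter the symptomatic stratum and dilute f_RS. The ratio f_RS/f_CS then drops for a reason unrelated to herbicide.
- Even with accurate reporting, symptomatic men in both groups may be mostly diseased and asymptomatic men mostly healthy. Extra disease caused by herbicide then moves men between strata without much change in the rate within each stratum.

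Section VI.A also gives a low f_RS two meanings. Read horizontally it suggests over-reporting; read vertically it lowers a herbicide relative risk. No rule says which reading governs, or which ratio prevails when f_RS/f_CS and f_R/f_C disagree.

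**Working it through.** The protocol gives no numerical value for these ratios, so there is no figure to reproduce. It gives no sensitivity or specificity for symptom reports either, and calls this "knowledge that may not exist in this study". The inputs below are therefore assumptions, apart from the symptom incidences in the second check.

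**Model.** D is disease prevalence, se the probability that a diseased man reports symptoms, and fp the probability that a healthy man does. Findings are assumed in 70% of diseased and 5% of other men. For each group:

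- P(S) = D·se + (1−D)·fp
- f_S = [.7·D·se + .05·(1−D)·fp] / P(S)
- f_Sbar = [.7·D·(1−se) + .05·(1−D)·(1−fp)] / [1−P(S)]
- f = .7·D + .05·(1−D), which contains neither se nor fp

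**Control group in (a) and (b)** (D = .05, se = .80, fp = .10): f_CS = .03275/.135 = .243; f_CSbar = .04975/.865 = .0575; f_C = .0825.

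**(a) No effect** (RANCH HAND D = .05, so f_R/f_C = 1.00).
- fp = .20: f_RS = .0375/.23 = .163; f_RS/f_CS = .67.
- fp = .30: f_RS = .04225/.325 = .130; f_RS/f_CS = .54. The asymptomatic ratio is (.04025/.675)/.0575 = 1.04.
- fp = .10, equal to controls: all ratios are 1.00.

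**(b) Disease doubled** (RANCH HAND D = .10, so f_R/f_C = .115/.0825 = 1.39).
- fp = .10, equal to controls: f_RS = .0605/.17 = .356; f_RS/f_CS = 1.47.
- fp = .20: f_RS = .065/.26 = .250; f_RS/f_CS = 1.03.
- fp = .30: f_RS = .0695/.35 = .199; f_RS/f_CS = .82. The asymptomatic ratio is (.0455/.65)/.0575 = 1.22.

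**(c) Accurate reporting in both groups** (se = .95, fp = .01).
- Disease 20% in controls, 40% in RANCH HAND: f_R/f_C = .31/.18 = 1.72. f_RS/f_CS = (.2663/.386)/(.1334/.198) = .690/.674 = 1.02. The asymptomatic ratio is (.0437/.614)/(.0466/.802) = .07117/.05810 = 1.22.
- Disease 1% in controls, 2% in RANCH HAND: f_R/f_C = .063/.0565 = 1.12, but f_RS/f_CS = (.01379/.0288)/(.007145/.0194) = .479/.368 = 1.30.

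**Second check, different model.** Section VI.B(2) illustrates misreporting "with the exposed population having a symptom incidence of 0.1 and the nonexposed population having a symptom incidence of 0.05". Take those as true symptom rates and assume findings in 50% of men with and 10% of men without a true symptom, in both groups. Then f_R/f_C = (.10×.5 + .90×.1)/(.05×.5 + .95×.1) = .14/.12 = 1.17. With no over-reporting both conditional ratios are exactly 1.00. If 10% of RANCH HAND men without a true symptom report one, and no controls do, f_RS = (.05 + .009)/(.10 + .09) = .311 and f_RS/f_CS = .311/.5 = .62.

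**Direction of the asymptomatic ratio.** Keep this second model with no effect. Let false reporting in RANCH HAND be 10% among men without findings and q1 among men with them. Then f_RSbar = .1(1−q1)/[.1(1−q1) + .9×.9], to be divided by f_CSbar = .1. The ratio is .90 at q1 = .20, 1.00 at .10 and 1.05 at .05.

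**The case against.** The strongest reply is that the plan does not depend on these two ratios. f_R/f_C is itself one of the five, and Section VI.A stresses the comparison of unconditional finding rates. The methods for questionnaire and examination data in Section VI.D (logistic models, McNemar's test, log-linear models) are not confined to symptom strata. Section VI.A looks for over-reporting in the horizontal comparisons. Section V.F reads symptom and finding combinations alongside verifiers, bias indicators and the exposure index, and Section VIII.D ties conclusions to a bias estimate. No section says that a low f_RS/f_CS is to be read as protection.

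Most of this stands, and it rules out several stronger readings that a reader might infer.

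- *Over-reporting makes both ratios look protective.* Not for the asymptomatic ratio, which is 1.04 in (a) and can fall on either side of 1.
- *Any over-reporting does the harm.* It must be greater in RANCH HAND. Equal over-reporting with no effect leaves every ratio at 1, and with disease doubled gives 1.47.
- *A true doubling is always reversed.* In this model it is masked at 20% v 10% and reversed at 30% v 10%.
- *Accurate reporting always drives the conditional ratios to 1.* The 1% v 2% example gives 1.30.

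The reply does not remove the point itself. The two ratios are expressly given the same standing as f_R/f_C as effect measures. The general safeguards may reduce or reveal over-reporting, but they do not turn a symptom-conditioned ratio into an exposure effect, and they do nothing for (c), where reporting is accurate.

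**Conclusion.** The point holds as a fault in how Section VI.A defines the herbicide effect. Neither f_RS/f_CS nor f_RSbar/f_CSbar estimates the effect of exposure on physical findings. When false symptom reports are more common in RANCH HAND, f_RS/f_CS is pushed down: .67 and .54 with no effect, and 1.03 and .82 with disease doubled, at 20% v 10% and 30% v 10% false symptoms. With common disease and accurate reporting both ratios understate the effect (1.02 and 1.22 against 1.72). The asymptomatic ratio has no determined direction of distortion.

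The sizes rest on assumed finding, reporting and disease rates. The structural result does not: f_R/f_C is free of symptom reporting among the men examined, and the conditional ratios are not. A reader might conclude that the study as a whole would miss a herbicide effect. The document does not support that, because f_R/f_C is already planned. The consequence is a set of nominally equal effect measures that can contradict one another, with no rule for choosing between them.

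**What to change.** In Section VI.A, remove f_RS/f_CS and f_RSbar/f_CSbar from the relative risks that define herbicide effects. State that f_R/f_C, over all examined men whatever symptoms they report, carries the examination effect. Keep f_RS, f_RSbar, f_CS and f_CSbar only to describe how well reported symptoms agree with findings.

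The cost is about one sentence of wording: no new data are needed and f_R/f_C is already in the plan. The change protects against symptom reporting only among the men who attend. If attendance itself depends on health or symptoms, f_R/f_C can still be biased, and that needs separate handling.

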The mortality status of the exposed cohort and the randomly selected controls will be ascertained using multiple techniques including; telephone interviews with subjects or their families, a review of Death Benefits claims filed with the VA, acquisition of death certificates on all known deceased individuals and reviews of autopsy reports and medical records whenever possible.

D. Morbidity Study

(1) General Considerations

A vigorous attempt to determine the morbidity experience of all exposed subjects and their primary controls will be undertaken using questionnaires, indepth personal interviews, and physical examinations. The schedule and method of contact with the study subjects is depicted in the Appendix, Table A-5.

(2) Questionnaire Methods

All exposed members and their matched primary controls will be offered a comprehensive personal and family health questionnaire via telephone. The telephone questionnaire is an important part of this study because non-compliance rates for the physical examination and its face-to-face interview are expected to be substantially greater than non-compliance with the telephone questionnaire. As depicted in the Appendix, Figure A-2, only an estimated 40% of the RANCH HAND population will participate in the examination, while 65% will respond to the telephone questionnaire. The information collected by questionnaire from these additional 309 individuals and their controls will provide valuable morbidity data which would otherwise be lost. The questionnaire (see Section XIII) will emphasize identification data, RVN tour history, dermatologic conditions, neuropsychiatric conditions, fertility aberrations, genetic defects in offspring, sensory defects, and personality factors, including assessments of risk-taking behavior. A review of medical systems will be included in the questionnaire, and will inventory symptoms prior to, during, and after duty in RVN as well as those currently manifested. The questionnaire will be limited to a 30-45 minute telephonic interaction with participants, and it will take 10 to 12 months to complete all initial questionnaires on both groups. It may be necessary to conduct the questionnaire in two telephone sessions to minimize fatigue and maximize response. The

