In the event that these more elaborate exposure index calculations are not feasible, two other approaches to the exposure estimate are available. A crude index can be constructed, based solely on the duration of RVN duty and the TCDD concentration of the herbicides used each year. While such an index would be less precise in defining an individual's estimated level of exposure, it would still permit valid comparisons within the RANCH HAND population. Stratification techniques could also be employed using AFSC and duration of exposure (RVN duty) as the grouping criteria.

VI. Statistical Methodology

A. Introduction

The design of the study is presented in schematic form in Figure 6. R' refers to the RANCH HAND personnel and C'' refers to the collection of all possible control individuals. As defined, R' and C'' will contain individuals who are deceased. Since C'' may be 15 to 25 times larger than R', a randomized subsample C' of C'' will be obtained. C' will be constructed from C'' by computer selection of the ten best matched controls for each exposed study subject. As previously noted, close matches will be made for the variables of age, AFSC, RVN tour length, and race. The matched controls will form ten cohorts, C₁ through C₁₀, as previously shown in Figure 1. A 50% random sample from each of the matched control sets of 10 will be selected for inclusion in the mortality assessment so that a group, C' is obtained that consists of 5 matched controls for each exposed subject. These controls will be designated as initial replacement candidates for the morbidity and followup studies. The remaining individuals in the control set will be additional replacement candidates in the event that replacement must occur beyond the members of the mortality set (see Figure 2). C' will be constructed without regard to whether the individual is currently living or dead so that an assessment of mortality can be accomplished.

Referring again to Figure 6, R and C indicate living RANCH HAND members and primary matched controls. If $m_{R'}$ is the proportion of R' found to be deceased, then,

$$R = (1 - m_{R'})R'$$

The questionnaire will provide data concerning specific symptoms and other findings in the R and C groups. Thus, various questionnaire finding rates in R, s_R , will be calculated and compared with the corresponding rates in C, s_C .

[figure not shown]

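### The rule that f_R/s_R below f_C/s_C points to over-reporting can put that label on a genuine, honestly reported effect

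*Protocol*

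**What the plan says.** Section VI.A defines the symptom rates from the questionnaire: "various questionnaire finding rates in R, s_R , will be calculated and compared with the corresponding rates in C, s_C". The finding rates come from the examination: "Rates of abnormal physical findings can be symbolically indicated as f_R and f_C for RANCH HAND and control groups respectively". It then explains that "the ratio f_R/s_R is the ratio of physical findings to reported symptoms in the RANCH HAND population", and gives the rule: "if f_R/s_R is less than f_C/s_C overreporting can be inferred". The conclusion that "overreporting can be inferred" carries no condition on whether findings are also raised in RANCH HAND.

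Two further indicators of over-reporting follow, both built on agreement within men. One is a finding rate in symptomatic RANCH HAND men (f_RS) below that in asymptomatic men (written here f_R,notS). The other is a ratio f_RS/f_R,notS that is lower than its control counterpart. One caveat closes the paragraph: "However, the existence of sub-clinical disease as the cause of these ratios cannot be excluded". The same section keeps the between-group ratios, including f_R/f_C and s_R/s_C, as measures "which are of central importance in defining herbicide effects".

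**The concern.** A ratio of two group rates is not a measure of unverified reporting. If exposure adds men who have both the symptom and the sign, numerator and denominator rise by the same amount, and any ratio above 1 falls. The rule then says over-reporting when nobody has over-reported.

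This matters because Section VIII.D names false positive response as the main bias expected and says that conclusions will be tied to an estimate of bias. An indicator that moves in the wrong direction under a real effect would feed that estimate, and Section VI.A does not say which reading prevails when its indicators disagree.

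**Working it through.** The protocol gives no numerical example of the rule and no values for f, so there is no figure to reproduce. The algebra is general; the rates below are assumed unless a source is named.

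**1. Condition for a false label.** Let reporting be honest in both groups. Let a genuine effect add d_f to the finding rate and d_s > 0 to the symptom rate, so f_R = f_C + d_f and s_R = s_C + d_s. Then

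(f_C + d_f)/(s_C + d_s) < f_C/s_C ⇔ s_C·d_f < f_C·d_s ⇔ d_f/d_s < f_C/s_C.

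If every excess case has both symptom and finding, d_f = d_s and the condition becomes f_C > s_C.

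**2. Equal increments.** Controls f_C = .30, s_C = .10: ratio 3.00. Add 5% with both: .35/.15 = 2.33, labelled over-reporting. Using the symptom rates of the example in Section VI.B(2) (.05 unexposed, .10 exposed) with an assumed f_C = .10: .10/.05 = 2.00 against .15/.10 = 1.50, again labelled.

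**3. Cases that mark the boundary.**
- Both rates doubled, .10 to .20 and .05 to .10: 2.00 against 2.00, not labelled although findings are commoner than symptoms.
- Increments +.10 and +.04 on .10 and .05: .20/.09 = 2.22 against 2.00, not labelled.
- Findings rarer than symptoms, .20 and .30, increments +.05 and +.10: .25/.40 = .625 against .667, labelled.

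**4. Diagnostic error equal in both groups.** Disease prevalence 5% in controls and 10% in RANCH HAND; finding sensitivity .90 and false-positive rate .10; symptom sensitivity .90 and false-positive rate .05. Controls: f = .10 + .05×.80 = .14 and s = .05 + .05×.85 = .0925, ratio 1.51. RANCH HAND: f = .18 and s = .135, ratio 1.33. Labelled.

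**5. What the other indicators say.** Return to .30 and .10. Suppose symptoms and findings are independent in controls, and the added 5% come from men who would have had neither.

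| | Both | Finding only | Symptom only | Neither |
|---|---|---|---|---|
| Controls | .03 | .27 | .07 | .63 |
| RANCH HAND | .08 | .27 | .07 | .58 |

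- f_R/s_R against f_C/s_C: 2.33 < 3.00, over-reporting.
- f_RS = .08/.15 = .53 against f_R,notS = .27/.85 = .32: not over-reporting.
- f_RS/f_R,notS = 1.68 against .30/.30 = 1.00 in controls: not over-reporting.
- f_R/f_C = .35/.30 = 1.17: findings raised.
- P(symptom and no finding): .15×(1 − .533) = .07 against .10×(1 − .30) = .07, no excess, which is correct.

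**6. Sampling.** In a simulation with 450 men per group (the number of pairs discussed in Section VI.F), f and s drawn independently, the inequality holds in about 50% of runs with no effect and no over-reporting. It holds in about 83% under the genuine effect .10 to .15 for findings and .05 to .10 for symptoms. A significance test, which an analysis plan could supply, would deal with the first figure but not the second, because there the expected ratio itself has moved.

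**The case against.** The strongest reply is that the wording is permissive and no analysis is dropped or adjusted when the inequality holds. The protocol still reports f_R/f_C and s_R/s_C, which are 1.17 and 1.50 in the main example. The two within-man indicators also contradict the label there, and with the same marginal rates they do so for any control f_CS from .30 to about .85. Section V.F(2) already relates symptoms to findings within each group and reads them with verifiers, bias indicators and the exposure index. All of this stands. It limits the harm to conflicting readings; it does not make the sentence correct. The caveat does not repair it either: Section V.F(2) describes sub-clinical disease as symptoms without correlated findings but with positive laboratory results, whereas the men at issue have both symptom and finding.

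A reader might infer three stronger things that the documents do not support.
- That findings being commoner than symptoms is enough for a false label. Step 3 shows it is neither sufficient nor necessary; the condition is d_f/d_s < f_C/s_C.
- That the rule would explain away a real effect. The other measures would still show it.
- That unequal attendance adds to the false labelling, since "only an estimated 40% of the RANCH HAND population will participate in the examination, while 65% will respond to the telephone questionnaire". Take 1,200 × .40 = 480 examinees and 1,200 × .65 = 780 responders, a difference of 300 (Section V.D(2) gives 309). With assumed symptom rates of 30% in examinees and 15% in the rest, s_R = (480×.30 + 300×.15)/780 = .242 rather than .30. f_R/s_R then rises by about 24%, away from the label. The protocol does not say that s_R in this ratio includes men who were not examined, and controls also miss examinations.

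An objection to the replacement index also stands: genuine symptoms without a detectable sign raise it too, and Section IV.E calls the neuropsychiatric symptoms largely subjective. In step 4, if symptom and finding errors are independent given disease status, the index moves from .95×.045 + .05×.09 = .047 in controls to .90×.045 + .10×.09 = .050 in RANCH HAND under honest reporting.

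**Conclusion.** The concern holds in limited form. As stated, the rule can call a genuine, honestly reported effect over-reporting, and it does so in expectation whenever the added finding rate divided by the added symptom rate is below f_C/s_C. The algebra needs only honest reporting and an effect that raises the symptom rate. The sizes shown (3.00 to 2.33, 2.00 to 1.50, 1.51 to 1.33) rest on assumed rates, and the disagreement with the within-man indicators in step 5 rests on independence in controls. The consequence is an indicator that can contradict the rest of Section VI.A with no stated way to resolve it, not a lost signal. The sentence should be changed.

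**What to change.** Remove the f/s ratio comparison as a basis for inferring over-reporting. In its place:

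- Among men with both questionnaire and examination, compare P(symptom and no finding) between groups: s_R(1 − f_RS) against s_C(1 − f_CS), with s taken in those same men. Using one set of men also removes any question about differing denominators.
- Read an excess in this index together with f_R/f_C, f_RS against f_R,notS, and the bias-indicator questions; do not infer over-reporting from it alone.
- Keep the caveat, stated for this index: genuine symptoms without detectable signs, including sub-clinical disease, raise it as well.

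The cost is a change of wording and one further tabulation of data already planned. The downside is that men with a questionnaire only do not contribute to the index; they still contribute to s_R/s_C.
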